#### Instructions:

*The Safe Departure Checklist is a standard set of data entered for every subject that engaged in laboratory smoking prior to their departure from the lab.*

## Appendix D: Data and Safety Monitoring Plan

## Responsibility of DSM

Because a Data and Safety Monitoring Board (DSMB) is only required for higher risk and/or multisite studies, and the proposed research is a single site pilot study with minimal risk, we do not include a formal DSMB. However, the Center for Tobacco Research in conjunction with the OSU Comprehensive Cancer Center does have a standing DSMB that we can utilize if the funding agency or the reviewers request one.

Co-PD/PIs [name] and [name] will be responsible for monitoring the safety and integrity of the research project, executing the DSM plan for the projects, and complying with the reporting requirements. They will also provide annual and interim progress reports to NCI and FDA.

With this project, the DSM will begin by reviewing the revised protocol and establishing guidelines for data and safety monitoring. This will include reviewing the standard procedures for day-to-day monitoring by the internal monitors, principal and co-investigators and study staff. DSM will include evaluating the progress of the trial; reviewing data quality, participant recruitment, and study retention; and examining other factors that may affect study outcome. The PIs will review major proposed modifications to the study prior to their implementation. They will also review the participants' ability to achieve the study requirements, and the rates of adverse events to determine whether there has been any change in participant risk. Their review will ensure that subject risk does not outweigh the study benefits. Following each DSMB meeting, a written report of their findings will be generated for the study record and provided to NCI and each site's Institutional Review Boards (IRB).

The specific DSM responsibilities will include the following:

- Review the research protocol, informed consent documents, and plans for data and safety monitoring;
- Evaluate the progress of the trial, including periodic assessments of data quality and timeliness, participant recruitment, accrual and retention, participant risk versus benefit, performance of the trial sites, and other factors that can affect study outcome;
- Consider factors external to the study that may be relevant, such as scientific or therapeutic developments, which could have an impact on the safety of the participants or the ethics of the study;
- Protect the safety of the study participants and report on the safety and progress of the trial;
- Make recommendations to the research team and sponsor, as required, concerning continuation, termination or other modification(s) to the trial.
- Ensure the confidentiality of the trial data and the results of monitoring;
- Assist on any problems with study conduct, enrollment, sample size, and/or data collection.
- Review data for accuracy and quality

Study progress reports will be prepared by the research team. These reports will include updates on the protocol, including revisions, enrollment progress and projections, retention, and safety data (description, severity, attribution, response, reporting and resolution of those events as well as if any events are unanticipated. If more than 10% of the participants experience an

adverse event during the course of the study then the PIs will consider suspension or discontinuation of the study.

## **Adverse Events**

Adverse events will be assessed by study staff at each follow-up visit via participant self-report and managed immediately. All adverse events will be reported to the OSU IRB. We will monitor for risk of smoking waterpipe by screening participants for general medical precautions (pregnancy, respiratory and cardiovascular disease). Participants will be given contact numbers of study personnel and Co-PD/PIs [name] and [name]. Any adverse events, breaks of confidentiality, or any other data or safety issues that arise will be discussed immediately between study personnel and the Co-PD/PIs.

Co-PD/PI [name] will be responsible for completing an Adverse Events Form should an event occur. She will report Serious Adverse Events to the OSU IRB within 24 hours of having received notice of the event. She will gather any information needed to investigate the event and to determine subsequent action. Any subsequent action will be documented and reported to the OSU IRB and the Program Officer at NIH. Adverse event reports will be reviewed annually with the OSU IRB to ensure participant safety.

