### II.3. How Can Sweet WP Tobacco Additives (Sugars and Glycerol) Contribute to Direct Harm?

WP tobacco smoking is associated with increased risk for lung, oral, esophageal, and head and neck cancers, and cardiovascular and pulmonary disease. Despite its growth in popularity over the past 30 years, there is little data available on the ingredients in WP tobacco, as the bulk of research has focused on toxicant yields in the smoke that is inhaled. WP tobacco is very different from cigarette or even pipe tobacco in that initial reports show that sweet tasting additives such as sugars and glycerol can comprise up to 70% of WP tobacco by weight.

Glycerol, which is not a sugar but still tastes sweet, can comprise 23–63% of the weight of the tobacco. Sugars such as sucrose, glucose, and fructose can also make up more than a third of WP tobacco weight. These same compounds are added to cigarettes, but at much lower levels (1-5%), to impart “smoothness” to the smoke and act as moisturizing agents, preservatives and solvents for flavor application. During the heating process, these sweet additives form volatile carbonyls, compounds that are known carcinogens and pulmonary toxicants such as acrolein, formaldehyde (IARC Group 1 carcinogen) and acetaldehyde (IARC Group 2B). During smoking, glycerol can dehydrate to acrolein; thus it is not surprising that, given WP tobacco is heavily fortified with glycerol, acrolein levels in WP smoke exceed those in cigarette smoke by a factor of 15 (see Table 3). Acrolein is ciliotoxic and can inhibit both the immune system and lung clearance. When heated, glycerol can also produce formaldehyde and acetaldehyde, which are both contributors to lung cancer in cigarette smokers and chronic obstructive pulmonary disease. Moreover, acetaldehyde increases the abuse liability of nicotine, contributing to the addictiveness of tobacco smoke. Short-term effects from exposure to these carbonyls results in pulmonary irritation and edema. After their authorities were extended to more novel tobacco products like WP, FDA proposed adding glycerol to the HPHC list.

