### III.B3. Aim 3 Sample

We will recruit a total of 60 healthy adult men and women with the goal of having complete data sets for 50 participants. Participants will meet the eligibility criteria shown in Table III.4. Established waterpipe smokers will be recruited from advertisements

*Table III.4. Participant inclusion and exclusion criteria.*

Inclusion	Justification for Inclusion
Sufficient understanding of consent form and study procedures	Necessary to ensure that participants are adequately informed about the study
Age 21-50 years old	Legally of age to purchase, use, and possess tobacco and provide informed consent
Experienced WP smokers defined as having smoked a WP at least 3 times per month in the last month	To assure that participants are experienced WP smokers, and increase the probability of subjects being able to comfortably smoke
Willing/able to abstain from nicotine product use for at least 12 hours prior to the laboratory visits	Necessary to normalize participants' willingness to smoke WP across visits
Willing to attend four laboratory sessions at the same time of day lasting approximately 3 h each	Necessary to complete all testing sessions and provide adequate power for data analysis
Read and speak English.	To ensure that participants are adequately informed about the study and can follow the
Exclusion	Justification for Exclusion
Evident intoxication on any visit	Intoxication would interfere with informed consent and study procedures
Exhaled breath CO > 10 ppm	Indicates recent combustible tobacco use.
Pregnancy (known or suspected), trying to become pregnant, breastfeeding, unwillingness to use contraception for the duration of the study.	Unethical to enroll pregnant or breastfeeding women for smoking research
Significant smoking-related disease (by history)	Unethical to enroll subjects with tobacco-related diseases

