## IV. Detailed Study Procedures for the Human Study (Aim 3)

Study subjects will participate in a series of 4 laboratory sessions, each visit separated by at least a week, in which they smoke one of 4 tobacco preparations (blinded) using the RWP2, shown in Figure II.1, in a randomly assigned sequence, using the block randomization method. Smoking sessions will be carefully standardized: they will take place in a controlled setting, individual roomsdesignated for smoking research with sufficient ventilation rate at the Center for Tobacco

Research) within one hour of the same time-of-day after overnight nicotine abstinence ( $\geq 8$  hours, exhaled CO  $\leq 10$  ppm^173).

Research staff will light and add the charcoal and record tobacco and charcoal weights. The research-grade waterpipes will be prepared by the laboratory staff, and participants will smoke ad lib to satiation. Participants will be limited to one bowl (15 g) of tobacco and one quick-light charcoal (~10 g).

Prior to the start of the first laboratory visit, a research assistant will explain the study to the participant and answer any questions they may have. The participants will give an exhaled breath sample into the handheld CO monitor to determine if they are eligible to participate in the laboratory smoking session. If the participant's exhaled CO concentration is less than or equal to 10 ppm) they are deemed eligible to participate further, and will be asked to read the informed consent form. Once all participant questions have been answered, the participants will each be asked to sign their consent to participate in the study. Each female participant of child-bearing age will be asked to provide a urine sample for use in conjunction with a "dip-stick" pregnancy test to determine participation eligibility. Female participants with a negative urine pregnancy will be eligible to participate if they provide written agreement (via signing the consent form) to use reliable contraception throughout their participation in the study.

Each participant will then be asked to provide a pre-smoking blood sample by venipuncture. If the phlebotomist is unable to take a sufficient blood sample (10 mL) from the participant, the participant will be deemed ineligible to participate further in the study. Participants will then answer demographic and tobacco use questions.

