**Spirometry.** Before and after smoking at each clinic visit, subjects will be asked to take a deep breath and then instructed to exhale forcefully into a handheld spirometer [NDD EasyOne Air Spirometer (NDD Medical Technologies, Andover, MA), or similar spirometer] according to American Thoracic Society Guidelines. This maneuver will be repeated up to 5 times in order to

ensure reproducible results. This non-invasive procedure will take up to 15 minutes to perform. Participants' height and weight will also be measured to calculate their expected spirometry measures as thresholds to use for determining potential impairment in lung function.

Safe Departure and Remuneration. At the end of each clinic session, research assistants will assess each of the participants for safe departure using a standardized checklist. An example checklist is provided in Appendix C. Visits 2-4 will be similar to the first visit, but the tobacco and use history data collection and the urine pregnancy test (women only) will not be repeated. Participants will receive \$50 for each laboratory visit and a bonus payment of \$50 for completing all four visits, for a total of \$250 at the conclusion of the last laboratory visit.

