## V. Risks, Benefits, Safety Plans

### V.1. Risks associated with the human study

Potential risks are minimal for the human participant study. Potential risks associated with the procedures and equipment that will be used to collect the exhaled breath CO, topography, and pulmonary data are minimal. Potential risks resulting from collecting blood samples include being unable to provide blood samples because forearm veins are not adequate, feeling light-headed or faint, nausea, dizziness, hematoma or bruising at or near the needle site. We minimize this risk by using certified technicians with extensive experience in collecting blood samples. However, if the participant does not feel comfortable for any reason and wants to end their participation in the study, he/she can do so at any time without penalty. Some of the survey questions may upset individuals; however, we have used these questions and procedures in many previous studies without upsetting participants.

There are no potential risks involved in the collection of waterpipe smoking topography, as the device does not change the resistance to draw or toxicity of the smoke inhaled. The data are acquired continuously to an electronic file, and may be displayed on a laptop screen that is not viewable by either participant. Therefore the possibility of the participant amplifying their puffing rate in order to see the on-screen response is eliminated.

Participants may feel hungry because they will not be permitted to eat until after their post-smoking lung function test is completed. Pulmonary function studies involve forceful respiratory maneuvers and occasionally people develop light-headedness during the procedures or soreness of the chest for a few days. Subjects will be seated and closely monitored by trained/certified personnel during those procedures.

The RWP that participants will smoke at the clinic is specially designed for investigational research only, and as such may have unknown health risks. Both the single- and dual-hose versions of the RWP have been used by participants in several previous studies.

A potential risk is loss of confidentiality. We have rigid procedures in place to protect against loss of confidentiality. Participant identifiers will be kept in a locked file cabinet. This study is not unlike our previous work investigating the efficacy of WP warning labels; we collect the

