## VII.2. Sample Size Justification.

Since Aims 1, 2, and 4 do not involve human subjects, we expect low variability across replicates. Thus, assuming a somewhat conservative coefficient of variation (CV) of 20% and log-normal outcomes, a total of **4 replicates per tobacco preparation** will provide 80% power to detect a two-fold change in the geometric means of two groups at a conservative two-sided Bonferroni-corrected type-I error rate of 0.0083.

Our sample size for Aim 3 was selected to ensure that we have adequate power to detect moderate effect sizes in our comparisons of topography outcomes. We made the following assumptions for the power analysis:

- Based on the intravariability data analysis for the RWP, correlation coefficients within subjects ( $r$ ) were assumed to be 0.6, 0.7 or 0.8.
- Small, medium, and large effect sizes ( $d$ ) of 0.2, 0.5, and 0.8 standard deviations.
- A two-sided, Bonferroni corrected type-I error rate of 0.0083.

Our power analysis, summarized in Table VII-5, revealed that a sample size of 43 subjects will provide over 80% power to detect a moderate effect size unless the within pair correlation is high (0.2 or 0.3) and the within participant correlation is modest (0.6). However, since this power analysis assumes complete follow-up, we will recruit **60 participants** to account for a possible attrition rate of 20%, and ensure the Latin square ordering is balanced across the four tobacco types.

Table VII.5. Estimated % power to for pairwise comparisons of tobacco preparations based N = 25 pairs (50 subjects).

$r$	$\rho$	Power		
		$d=0.2$	$d=0.5$	$d=0.8$
0.6	0.1	0.108	0.803	0.998
	0.2	0.097	0.759	0.996
	0.3	0.088	0.717	0.994
0.7	0.1	0.153	0.918	> 0.999
	0.2	0.138	0.889	> 0.999
	0.3	0.125	0.857	0.999
0.8	0.1	0.255	0.989	>0.999
	0.2	0.228	0.981	>0.999
	0.3	0.207	0.971	>0.999

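### No scheduled question covers adverse events that begin after a participant's last attended session, so these can go uncounted in the safety review

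*Combined protocol and SAP*

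**What the plan says.** Appendix D (Adverse Events) sets the timing and method of collection: "Adverse events will be assessed by study staff at each follow-up visit via participant self-report and managed immediately". It also gives participants contact numbers for study staff and the co-PIs, and sends all adverse events to the IRB.

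Appendix D (Responsibility of DSM) sets the trigger. If more than 10% of participants have an "adverse event during the course of the study then the PIs will consider suspension or discontinuation of the study". There is no formal monitoring board. The co-PIs monitor safety and review adverse-event rates.

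Section IV gives the schedule: "Study subjects will participate in a series of 4 laboratory sessions, each visit separated by at least a week". The final payment is made when the last laboratory visit ends. Also: "At the end of each clinic session, research assistants will assess each of the participants for safe departure using a standardized checklist". The visible text describes no visit, call or survey after that.

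On numbers, section III.B3 says "We will recruit a total of 60 healthy adult men and women with the goal of having complete data sets for 50 participants", and section VII.2 sets recruitment "to account for a possible attrition rate of 20"%.

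**The concern.** The wording in Appendix D assumes a visit that follows each exposure. For sessions 1 to 3 the next session can serve. For a participant's last attended session nothing does. This affects everyone who completes, after session 4, and everyone who stops early, after whichever session was their last. It includes anyone who stops because of a reaction.

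The plan itself expects at least one effect to last beyond the visit. Section V.1 warns that spirometry may cause "soreness of the chest for a few days".

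The co-PIs' review of rates, the IRB and annual reports, and the 10% trigger can act only on events that staff learn of. An unsolicited late event makes the count too low and never too high.

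**Working it through.** **Step 1. Read the collection rule against the schedule.** The term follow-up visit is not defined, and it can be read in two ways.
- *Sessions 2 to 4 only.* Events after sessions 1, 2 and 3 are asked about at the next session. Nothing is asked at or after session 4 beyond the departure checklist.
- *Every laboratory session.* Events during session 4 are also covered.

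On both readings, an event that begins after the last attended session is not asked about.

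**Step 2. Count the sessions affected.** Each of the 60 recruits has exactly one last session.
- All complete: 60 / (60 × 4) = 60/240 = 25% of sessions have no later visit.
- 20% (12 people) leave after session 1: 60 / (48 × 4 + 12) = 60/204 = 29%.

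**Step 3. Turn the trigger into a count.** The 10% is a chosen threshold with no derivation, so there is no figure to reproduce. More than 10% of 60 is at least 7 (11.7%). More than 10% of 50 is at least 6 (12%).

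**Step 4. Illustrate the effect on the trigger.** The documents give no adverse-event rate, so everything from here is assumed. Let p be the chance that a session is followed by an event that starts after the participant has left. Take independent sessions, nobody leaving early, and an event known only if a later contact asks.
- All four sessions asked about: q = 1 − (1 − p)^4
- Last session omitted: q = 1 − (1 − p)^3
- Participants with a known event: X ~ Binomial(60, q); the trigger is X ≥ 7

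| p | q, all four | q, last omitted | Expected count | P(X ≥ 7) |
|---|---|---|---|---|
| 2% | 0.0776 | 0.0588 | 4.7 vs 3.5 | 0.18 vs 0.06 |
| 3% | 0.1147 | 0.0873 | 6.9 vs 5.2 | 0.54 vs 0.27 |
| 5% | 0.1855 | 0.1426 | 11.1 vs 8.6 | 0.95 vs 0.77 |
| 10% | 0.3439 | 0.2710 | 20.6 vs 16.3 | >0.999 vs 0.999 |

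With 50 participants and a threshold of 6, the 5% row gives 0.92 against 0.74.

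**Step 5. Relax the two assumptions that enlarge the gap, at p = 5%.**
- *Half of last-session events are self-reported.* q = 1 − 0.95^3 × 0.975 = 0.164, so P(X ≥ 7) = 0.88 against 0.95.
- *The same people tend to react.* Use a beta-binomial with within-person correlation 0.6: a = 0.05 × 0.4/0.6 = 0.0333 and b = 0.95 × 0.4/0.6 = 0.6333. The chance of at least one event is 0.0890 over four sessions and 0.0806 over three. P(X ≥ 7) is 0.28 against 0.21. At correlation 0.8 it is 0.11 against 0.09, and at 1 there is no difference.

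**The case against.** **Late events are not necessarily lost.** Participants hold contact numbers, reminder contacts are planned (section III.B3), and staff review retention regularly, for example weekly. These routes could surface an event, so treating every unsolicited event as unknown is the extreme case. This stands, and it is why 0.77 is a low-end figure under its assumptions. None of these routes is a scheduled adverse-event question, so the gap remains.

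**In-session reactions are well covered.** Staff watch through a window, spirometry is repeated after smoking, and the departure checklist is completed. This also stands. The point concerns only events that start after departure. On those the plan's evidence is thin: the effect it says lasts for days is minor soreness from spirometry. Section II.3 says "Short-term effects from exposure to these carbonyls results in pulmonary irritation and edema", but that describes carbonyl exposure in general and does not put onset after the visit.

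**A reader might infer more than the documents support.**
- *That a yes on the departure checklist is not counted as an adverse event.* The form in Appendix C is an example carrying another study's title and IRB number, and part of that appendix is not in the text available. Appendix D sends all adverse events to the IRB without excluding any by source. The documents do not settle this either way.
- *That the remedy is to count every checklist symptom.* If another 5% per session answered yes (assumed, independent), the chance of any event over four sessions would be 1 − (0.95 × 0.95)^4 = 0.337, about 20 of 60 people. The trigger would be reached with probability above 0.999 and would tell the PIs little.
- *That the undercount falls hardest on one tobacco.* The trigger counts participants, not tobaccos. No comparison of adverse events by tobacco is planned, and session order is randomised and meant to be balanced.

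**Other documents may close the gap.** The cancer centre's monitoring plan cited in section IX is not shown, and Appendix D says monitoring begins by setting guidelines. Either could add a closing contact.

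**Conclusion.** The gap is real on the visible text: nothing scheduled asks about events that begin after a participant's last attended session. It can only lower the adverse-event count.

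Its size cannot be fixed from the documents. At an assumed 5% per session, the loss in the chance of reaching 7 of 60 runs from 0.95 against 0.77 (independent sessions, no self-reports), through 0.95 against 0.88 (half of last-session events self-reported), to 0.28 against 0.21 (within-person correlation 0.6). The effect almost disappears at high event rates or when the same people always react.

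The consequence is limited. Crossing 10% obliges the PIs only to consider suspension, serious reactions during a session would be seen, and no outcome analysis depends on the trigger. This is an inexpensive improvement for the sponsor to consider. It is not a flaw that threatens the trial's safety or its conclusions.

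**What to change.** In Appendix D (Adverse Events), replace the phrase giving the timing of assessment with: *at every laboratory session, and by one call or text about a week after each participant's last attended session, including those who stop early (asking about adverse events and the reason for stopping)*.

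The cost is one amendment to Appendix D and about 60 brief contacts, made by the call, text and email routes already planned for reminders. A few more events, mostly mild, will be logged and sent to the IRB. The trigger may be reached somewhat sooner: at the assumed 5% per session with independent sessions, 11.1 rather than 8.6 participants with an event are expected if everyone replies. Some who stop early will not reply, so the gap narrows but does not close.
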